8. RESEARCH QUESTION AND OBJECTIVES

The purpose of the CIBINQO[™] Pregnancy Registry is to describe and compare the proportion of adverse maternal, fetal, and infant outcomes among women with moderate-to-severe AD who are exposed to CIBINQO during pregnancy and women with moderate-to-severe AD who are unexposed to CIBINQO during pregnancy.

Primary objective:

• To estimate the crude proportion of maternal, fetal, and infant outcomes of women with moderate-to-severe AD who are exposed to CIBINQO during pregnancy and women with moderate-to-severe AD who are unexposed to CIBINQO during pregnancy.

Secondary objective:

• To compare the proportion of maternal, fetal, and infant outcomes between women with moderate-to-severe AD who are exposed to CIBINQO during pregnancy and women with moderate-to-severe AD who are unexposed to CIBINQO during pregnancy, if sample size permits.

The following outcomes will be assessed:

- MCM
- Minor congenital malformations
- SAB
- Stillbirth
- Elective termination
- Preterm birth
- SGA
- Postnatal growth deficiency
- Infant developmental delay

Refer to Section 9.3.2 for the definitions of these outcomes.

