9. RESEARCH METHODS

9.1. Study design

The CIBINQO[™] Pregnancy Registry is a US-based, prospective, observational cohort study designed to evaluate the association between CIBINQO exposure during pregnancy and subsequent maternal, fetal, and infant outcomes. Participation in the registry is voluntary and participants can withdraw their consent to participate at any time. Data will be collected from enrolled pregnant women and the healthcare providers (HCPs) involved in their care or the care of their infants, if applicable. The registry is observational in design; the schedule of office visits and all treatment regimens will be determined by HCPs. Only data that are typically documented in participants' medical records during the course of medical care will be collected. No additional laboratory tests or HCP assessments will be required as part of this registry. A VRCC will be used for data collection.

All assessments described in this protocol are performed as part of routine clinical practice or standard practice guidelines for the patient population and HCP specialty in the US.

The CIBINQO[™] Pregnancy Registry will be launched following protocol endorsement from the FDA and institutional review board (IRB) approval of the protocol. Enrollment of women in the registry is expected to begin in 2023 and end in March 2026. Data collection will be conducted through December 2027. Participants will be followed for 12 months after delivery for live births or until the onset of an adverse pregnancy outcome (SAB, still birth, or elective termination) for non-live births.

[figure not shown]

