Minor congenital malformation	An anomaly or abnormality of body structure that is present at birth, is of prenatal origin (i.e., birth defect), poses no significant health problem in the neonatal period, and tends to have limited social or cosmetic consequences for the affected individual (CDC, 2020)	The registry defines and codes minor congenital malformations with criteria specified as defined by CDC (CDC, 2019). The same process for a djudicating MCMs will be used to a djudicate minor congenital malformations.		
Spontaneous a bortion (SAB)	An involuntary fetal loss or the expulsion of the products of conception occurring at <20 gestational weeks	Section 9.3.3 provides information on the methods used to calculate gestational age.		

Table 1. Outcome Definitions and Ascertainment

Outcome	Definition	Ascertainment
Stillbirth	As defined by the ACOG, an involuntary fetal loss occurring at ≥ 20 gestational weeks or, if gestational age is unknown, a fetus weighing ≥ 350 g(ACOG, 2020)	Section 9.3.3 provides information on the methods used to calculate gestational age.
Elective termination	A voluntary fetal loss or interruption of pregnancy that occurs for any reason, including but not limited to for the preservation of maternal health or due to fetal abnormalities	-
Preterm birth	A live birth occurring at <37 gestational weeks	Section 9.3.3 provides information on the methods used to calculate gestational age.
Small for gestational age (SGA)	Birthweight <10th percentile for sex and gestational age using standard growth charts for full and preterm live-born infants (Battaglia & Lubchenco, 1967)	For the determination of SGA, the registry will utilize the sex-specific international growth reference standards from the INTERGROWTH-21st for those born between 24 ^{0/7} and 42 ^{6/7} gestational weeks (Villar et al, 2014; Villar et al, 2016). The INTERGROWTH-21st standards are the latest a vailable global reference standards, representing contemporary information from an international, multiethnic, diverse population, and have been specifically developed for modern research.

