9.5. Study size

9.5.1. Assessment of study feasibility

To assess the feasibility of this study, data-driven assumptions regarding the prevalence of moderate-to-severe AD, pregnancy, and CIBINQO uptake were made to estimate the number of women who will potentially be exposed to CIBINQO during pregnancy. The prevalence of AD overall among women of childbearing age was assumed to be 5.5%, with 50% having moderate-to-severe AD (Barbarot et al, 2018; Fuxench et al, 2019; Chidwick et al, 2020); the proportion receiving pharmacotherapy was assumed to be 70% (Beck et al, 2014; Boguniewicz et al, 2017; Napolitano et al, 2021). It was further assumed that 3% of those receiving pharmacotherapy would be treated with CIBINQO (Pfizer internal projections). These assumptions were applied to the population of women of childbearing potential in the US (approximately 74.5 million; US Census Bureau, 2020), which yielded an estimated 43,038 women of childbearing potential who will potentially receive CIBINQO each year. After application of the general fertility estimates in the US (56.0 pregnancies per 1,000 women aged 15 to 44 years; Osterman et al, 2022) and the proportion of pharmacotherapy discontinuation during pregnancy among women with moderate-to-severe AD (10% assumed percentage of discontinuation due to severity of symptoms and risk during pregnancy), it was estimated that 6,507 women may potentially be exposed to CIBINQO during pregnancy over the course of 3 years. Given a 3% MCM prevalence among live births (CDC, 2008) in the US general population, these CIBINQO-exposed pregnancies can be expected to result in approximately 195 live births with MCM.

If the registry were to capture one fourth of these births, a total of 49 lives births with MCM may be enrolled.

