Stillbirth	0.596%	MacDorm an & Gregory, 2015	Live births and stillbirths	1:1	13610	4142	2159	1389	999	769	619	516	440
Elective termination	18.6%	Jatlaoui et al, 2019	Live births	1:1	343	100	50	31	21	15	12	9	NA ¹
Preterm birth	8.47%	Martin et al, 2021	Singleton live births	1:1	868	260	134	85	60	46	36	30	25
SGA	10.0%	By definition	Singleton live births	1:1	721	215	110	70	49	37	29	24	20
Postnatal growth deficiency	10.0%	By definition	Singleton live births	1:1	721	215	110	70	49	37	29	24	20

Table 4.	Sample Size Calculations for the Secondary Objective
----------	------------------------------------------------------

CDC = Centers for Disease Control; MCM = major congenital malformation; NA = not a vailable; reference prevalence = prevalence of outcome in general population for pregnant women of any age; RR = relative risk; SAB = spontaneous a bortion; SGA = small for gestational age.

The outcome infant developmental delay is not listed in the table because a published reference rate is not available.

Sample size calculations were performed in SAS (version 9.4) for the outcomes of interest using Fisher's exact conditional test with Walters normal approximation method, and assuming a power of 80% and a 2-sided α level of 0.05.

1 For elective termination, a relative risk of 5.5 with a reference prevalence of 18.6% in the unexposed cohort would result in an estimate above 100% in the exposed cohort.

Outcomes	Power Estimate
МСМ	80%
SAB	>80%
Stillbirth	21.4%
Elective termination	>80%
Preterm birth	>80%
SGA	>80%
Postnatal growth deficiency	>80%

Table 5.Power Calculations

MCM = major congenital malformation; SAB = spontaneous abortion; SGA = small for gestational age.The outcome infant developmental delay is not listed in the table because a published reference rate is not available.

Power calculations were performed in SAS (version 9.4) for the outcomes of interest using Fisher's exact conditional test with Walters normal approximation method, and assuming a sample size of 265 per c ohort, a relative risk of 3.0 and a 2-sided α level of 0.05.

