Spontaneous abortion (SAB)	SABs among women with pregnancy outcome data who are enrolled (and exposed, if applicable based on cohort) prior to 20 gestational weeks	Women with pregnancy outcome data who are enrolled (and exposed, if a pplicable based on cohort) prior to 20 gestational weeks				
Stillbirth	Stillbirths a mong women with pregnancy outcome data	Women with pregnancy outcome data				
Elective termination	Elective terminations among women with pregnancy outcome data	Women with pregnancy outcome data				
Preterm birth	Singleton preterm live births without MCMs among women with pregnancy outcome data who are enrolled (and exposed, if applicable based on cohort) prior to 37 gestational weeks	Singleton live births without MCMs among women with pregnancy outcome data who are enrolled (and exposed, if a pplicable based on cohort) prior to 37 gestational weeks				

Table 6.Calculation of Outcome Proportion

Outcome	Numerator	Denominator
Small for gestational age (SGA)	Singleton live births without MCMs who are SGA among women with pregnancy outcome data	Singleton live births without MCMs with weight data a mong women with pregnancy outcome data
Postnatal growth deficiency (at 4 and 12 months)	Singleton infants without MCMs who were not born preterm or SGA with postnatal growth deficiency based on weight/length/head circumference among infants with weight/length/head circumference data at the time point	Singleton infants without MCMs who were not born preterm or SGA with weight/length/head circumference data at the time point
Infant developmental delay (at 4 and 12 months)	Infants without MCMs who were not born preterm with developmental deficiency in a particular category among infants with developmental milestone data for the category at the time point	Infants without MCMs who were not born preterm with developmental milestone data for the category at the time point

 Table 6.
 Calculation of Outcome Proportion

MCM = major congenital malformation; SAB = spontaneous abortion; SGA = small for gestational age.

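### Table 6 confines postnatal growth and developmental delay to infants free of MCM, preterm birth and (for growth) SGA, so these two endpoints cannot reflect drug effects acting through those outcomes; unrestricted results should be reported beside them

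*Protocol*

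**What the plan says.** The registry is "designed to evaluate the association between CIBINQO exposure during pregnancy and subsequent maternal, fetal, and infant outcomes" (Protocol 9.1). The secondary objective in section 8 is "To compare the proportion of maternal, fetal, and infant outcomes between women with moderate-to-severe AD who are exposed to CIBINQO during pregnancy" and unexposed women, if sample size permits. MCM, preterm birth, SGA, postnatal growth deficiency and infant developmental delay all stand in the same list of outcomes.

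Table 6 in section 9.7.2 fixes the denominators for the two infant endpoints at 4 and 12 months:

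- Postnatal growth deficiency: "Singleton infants without MCMs who were not born preterm or SGA with weight/length/head circumference data at the time point".
- Infant developmental delay: "Infants without MCMs who were not born preterm with developmental milestone data for the category at the time point". SGA infants are not excluded here.

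The restriction appears only in Table 6:

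- Table 1 (9.3.2) defines both endpoints by chronological age and does not exclude infants with MCM, preterm birth or SGA.
- Section 9.7.1 excludes multiple gestations for growth but none of the three conditions.
- Tables 3 and 4 (9.5.2) give the denominator for postnatal growth deficiency as "Singleton live births", at a 10% reference prevalence.
- Section 9.9 (limitations) does not mention the restriction, and no rationale is given elsewhere.

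**The concern.** MCM, preterm birth and SGA occur after exposure, and the registry studies each as a possible drug effect. Removing affected infants from the growth and developmental denominators has two consequences.

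First, any effect of exposure on growth or development that runs through one of those conditions is removed from the endpoint by construction. What is left is the association among infants who escaped all of them.

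Second, if exposure changes the frequency of the three conditions, the infants left in the exposed and unexposed cohorts have passed through different selection. The stabilized weights in 9.7.3 use baseline covariates only, so they do not correct for selection on later events. The documents do not settle the direction of that bias.

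Nothing listed restores these infants. The sensitivity analyses named in 9.7.4 do not, although that list is open-ended. The supplementary analyses in the abstract add back participants left out of the analysis population, and MCM, preterm birth and SGA are not criteria of that population. At stake is how the 4- and 12-month growth and developmental results can be read: they describe a selected subset, while the objective speaks of infant outcomes in each cohort.

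**Working it through.** **Inputs from the protocol**

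- MCM 3.0% of live births: "Given a 3% MCM prevalence among live births (CDC, 2008) in the US general population" (9.5.1; also Tables 3 and 4).
- Preterm birth 8.47% of singleton live births (Tables 3 and 4).
- SGA 10.0% by definition: "Birthweight <10th percentile for sex and gestational age using standard growth charts for full and preterm live-born infants" (Table 1; Tables 3 and 4).
- Postnatal growth deficiency 10.0% of singleton live births (Tables 3 and 4).
- 265 live births per cohort for the secondary objective; two-sided alpha 0.05; 80% power; 1:1 (9.5.2).

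**Step 1. Reproduce the plan's own figure.** Table 4 uses Fisher's exact test with the Walters approximation:

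power = Φ( √(2n) × [asin√(p2 − 1/(2n)) − asin√(p1 + 1/(2n))] − 1.96 ).

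With p1 = 0.10 and p2 = 0.30, power is 79.9% at n = 69 and 80.5% at n = 70, so n = 70, as stated. RR 2.5, 2.0 and 1.5 give 110, 215 and 721, also as stated. MCM at RR 3 gives 265, as stated. The sizing for growth deficiency is therefore correct for all singleton live births, which is not the Table 6 denominator.

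**Step 2. Share of infants removed at the reference rates, if independent**

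- Growth: 1 − 0.97 × 0.9153 × 0.90 = 0.201.
- Development: 1 − 0.97 × 0.9153 = 0.112.
- Range for growth: from 10.0% (the three conditions fully nested, so the largest governs) to 3.0% + 8.47% + 10.0% = 21.5% (no overlap).

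**Step 3. Infants left, from 265 per cohort**

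- Growth: 265 × 0.799 = about 212.
- Development: 265 × 0.888 = about 235.
- Power for growth deficiency at RR 2 (10% vs 20%): 88% with 265, 79% with 212. At RR 3 it is above 99% either way.

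These counts treat all 265 as singletons with complete follow-up. The 265 was derived for MCM under first-trimester exposure, whereas growth and development use exposure at any point, so actual numbers will differ.

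**Step 4. Differential removal if exposure raises the three outcomes.** If exposure multiplies each rate by k, the share of exposed infants removed from the growth analysis is 1 − (1 − 0.03k)(1 − 0.0847k)(1 − 0.10k). The unexposed share stays at 20.1% for growth and 11.2% for development.

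| k | Removed from growth, exposed | Removed from development, exposed |
|---|---|---|
| 1.5 | 29.1% | 16.6% |
| 2 | 37.5% | 21.9% |
| 3 | 52.5% | 32.1% |

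**Step 5. Illustration of the mediated effect.** The deficiency risks here are assumptions and are not in the protocol: 8% in retained infants of both cohorts (no direct effect), and 30% or 50% in excluded infants.

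- k = 2, 30%: exposed 0.375 × 0.30 + 0.625 × 0.08 = 0.163; unexposed 0.201 × 0.30 + 0.799 × 0.08 = 0.124; RR in all singletons 1.31.
- k = 2, 50%: 0.238 / 0.164 = RR 1.45.
- k = 1.5: RR 1.16 to 1.23. k = 3: RR 1.57 to 1.83.

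Under these assumptions the Table 6 RR is 1.00 in every case.

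A narrower example doubles SGA alone, from 10% to 20%. With assumed deficiency risks of 40% in SGA and 7% in other infants, the RR in all infants is (0.2 × 0.40 + 0.8 × 0.07) / (0.1 × 0.40 + 0.9 × 0.07) = 0.136 / 0.103 = 1.32. With 25% and 8% it is 0.114 / 0.097 = 1.18. The RR among non-SGA infants is 1.00 both times.

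**The case against.** **The effects are not hidden from the registry.** MCM, preterm birth and SGA each have their own row in Table 6 and their own RR under 9.7.3. A doubling of SGA would have about 88% power at 265 per cohort (87% at 257, after removing 3% with MCM). A reader might infer that a drug impairing fetal growth would be reported as reassuring for all exposed infants. The documents do not support that, because the SGA result would stand in the same report. This objection stands and confines the point to the growth and developmental endpoints.

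**The follow-up has other uses.** Infants are followed: "Participants will be followed for 12 months after delivery for live births". A reader might infer that the restriction largely wastes that year. It does not. Section 9.9 relies on the same follow-up for malformations not visible at birth, and SGA infants stay in the developmental denominator, so effects on development through SGA remain visible there unless the infant also has an MCM or was born preterm.

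**The restricted question is coherent.** Table 1 judges both endpoints by chronological age, so preterm infants can be counted as deficient or delayed because they were born early. Excluding SGA avoids counting again infants already recorded as small at birth. This is a fair reason to keep a restricted analysis. It does not explain dropping infants with MCM, and the protocol does not state it. It makes replacing the restricted analysis, or correcting age as the main approach, a debatable choice of estimand.

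**The added analysis may not detect much.** By the same formula, power at 265 per cohort is about 18% for 10.3% vs 13.6% and about 7% for 9.7% vs 11.4%. That stands: the gain is mainly in what the estimate describes.

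**The SAP could add it.** It could: these are secondary outcomes and the sensitivity list is open. But the protocol already fixes one denominator, and that one disagrees with its own sizing tables.

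**Conclusion.** The point holds for two endpoints. As Table 6 stands, postnatal growth deficiency and developmental delay are conditional on the absence of post-exposure outcomes that the drug may affect. They cannot reflect effects acting through MCM, preterm birth or (for growth) SGA, and the retained groups may be differently selected in a way that the planned weights do not address.

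At the reference rates the restriction removes about 20% of singleton live births from growth under independence, and about 11% of infants from development. It also departs from the denominator used in Tables 3 and 4. The size of any missed mediated effect cannot be fixed from the documents: the RRs of 1.16 to 1.83 rest on assumed risks and assumed drug effects. Only the direction follows, if excluded infants have the higher risk and exposure raises the excluded conditions. This is an inexpensive improvement to what is reported and does not invalidate the registry's infant findings.

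**What to change.** In Table 6, add two rows and report them beside the existing ones, with proportion and RR:

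- postnatal growth deficiency at 4 and 12 months in all live-born singletons with the relevant measurement;
- developmental delay at 4 and 12 months in all live-born infants with milestone data for the category.

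Use the Table 1 definitions unchanged. Gestation-corrected age for preterm infants can be an optional sensitivity analysis, since it departs from the chronological-age definitions. Label the existing rows as conditional on no MCM, no preterm birth and, for growth, no SGA.

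The cost is the Table 6 wording and one extra set of tables. No new data are needed: the Infant Outcomes Form is requested for each live-born infant (9.2) and gestational age at outcome is collected (9.4). The downside is that the unrestricted result mixes direct effects with those acting through preterm birth, SGA and MCM, and includes misclassification of preterm infants judged by chronological age. That is why both sets should be shown.

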9.7.4. Subgroup and sensitivity analyses

If sample size permits, subgroup analyses will be conducted that consider the timing of exposure (earliest trimester of exposure), extent of exposure (cumulative dose during pregnancy or relevant exposure window), number of systemic therapy exposures during pregnancy (1 or \geq 1), and maternal age group at conception (<18, 18 to <35, 35 to <45, and \geq 45 years). The analysis of MCM will be stratified by earliest trimester of exposure, with a primary focus on exposure during the first trimester.

Sensitivity analyses will also be conducted to examine the extent to which changes in certain methods or assumptions affect the results. The sensitivity analyses may include, but are not limited to:

- Applying a stricter definition of prospective enrollment to the analysis of MCM. For this analysis, women who enroll or make initial contact with the registry prior to diagnostic prenatal testing will be considered prospectively enrolled, and women who enroll or make initial contact with the registry after diagnostic prenatal testing, regardless of the results, will be considered retrospectively enrolled.
- Accounting for the correlation between previous and subsequent pregnancies in the same woman and multiple gestation pregnancies using mixed models in the analysis of the outcome.
- Including the propensity score and a variable for treatment in an unweighted generalized linear model using a binomial family and a log (RR) link to test the robustness of IPTW.
- Applying inverse probability of censoring weights to account for potential informative censoring due to differential loss to follow up.

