- Are not exposed to teratogens or investigational medications during pregnancy
- Are not multiple gestation pregnancies for the analyses of preterm birth, SGA, and postnatal growth deficiency

Demographic and baseline characteristics will be summarized with descriptive statistics for each cohort, and balance between cohorts will be assessed using standardized differences. For each continuous variable, the number of observations, median, mean, standard deviation, minimum, and maximum will be reported. For each categorical variable, the frequency and percentage in each category will be reported. Baseline data will be presented before and after applying inverse probability of treatment weights (IPTW) to assess the balance across treatment groups.

The proportion of the outcomes of interest will be calculated and, if sample size permits, compared between the exposed and unexposed cohorts. For each outcome, if the number of events permits, crude and adjusted results will be presented. Relative risks (RR) will be reported along with their 95% confidence intervals. Exact methods will be used to calculate crude (unadjusted) RRs for all outcomes. Adjusted methods will incorporate weights estimated using stabilized IPTW to balance the cohorts with regard to the measured covariates. For each outcome, a weighted generalized linear model using a binomial family and a log (RR) link will be employed to estimate an adjusted RR.

If sample size permits, subgroup analyses will be conducted that consider the timing and extent of exposure, number of systemic therapy exposures during pregnancy, and maternal

age group at conception. Supplementary analyses will be conducted that include participants who were excluded from the analysis population. Sensitivity analyses will also be conducted to examine the extent to which changes in certain methods or assumptions affect the results.

Milestones:

Enrollment of women in the registry is expected to begin in January 2023 and end in March 2026. Data collection will be conducted through December 2027, with the final study report planned for December 2028.

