9.2. Setting

The study population will include pregnant women of any age who meet the eligibility criteria for inclusion. The exposed cohort will include women who are exposed to CIBINQO at any time during pregnancy. All pregnant women exposed to CIBINQO will be eligible to participate in the registry, but the analysis population will be limited to women with moderate-to-severe AD. The primary comparator group will include women with moderate-to-severe AD who are unexposed to CIBINQO during pregnancy. If sample size permits, a secondary comparator group will include the subset of women with moderate-to-severe AD who are exposed to other chronic systemic treatments that are not JAK inhibitors (e.g., dupilumab) during pregnancy.

Pregnant women who are interested in participating will self-enroll in the registry through the web-based/mobile application or by calling the VRCC. To enroll, each woman will answer a series of screening questions to assess her eligibility. If eligible, she will be asked to provide informed consent, her primary contact information, alternate contact information for a family member or friend, contact information for HCPs who are/will be involved in her care or the care of her infant, and medical releases to allow these HCPs to provide data to the registry.

Enrolled pregnant women and the HCPs involved in their care or the care of their infants, if applicable, will serve as data reporters to the registry. It is anticipated that the majority of obstetric data will be collected from the pregnant woman's obstetric HCP (e.g., obstetrician, family practitioner, general practitioner who provides care during pregnancy), and that the majority of pediatric data will be collected from the infant's pediatric HCP (e.g., pediatrician, family practitioner, general practitioner who provides pediatric care). After enrollment, the registry may also request data from other HCPs involved in the woman's or infant's care (e.g., prescriber, specialist) or from additional HCPs who were not identified at enrollment (e.g., if a woman does not know who her pediatric HCP will be at the time of enrollment) after appropriate medical release is obtained from the woman.

Figure 1. Study Flow Chart

^a Time to product elimination (5 times terminal half-life); CIBINQO half-life = 5 hours; therefore, time to elimination = 1 day

^b If a participant is exposed to the product during this time period, she will be considered exposed during pregnancy

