9.2.1. Inclusion criteria

Participants must meet all of the following inclusion criteria to be eligible for inclusion in the study:

- Women of any age who are currently or recently pregnant (recently pregnant defined as enrollment within 1 year of pregnancy outcome)
 - Only prospectively enrolled patients (i.e., women who are currently pregnant at enrollment) will be included in the main analysis population
- Consent to participate in this study and evidence of a personally signed and dated informed consent document indicating that the patient (or a legally acceptable representative) has been informed of all pertinent aspects of the study
- Authorization for her HCP(s) to provide data to the registry
- Exposed cohort only: Must receive at least one dose of CIBINQO at any time during pregnancy (from the DOC to pregnancy outcome) or prior to pregnancy (within 1 day prior to the DOC).
- Comparator cohort only: Must have a diagnosis of moderate-to-severe AD at any time prior to pregnancy outcome.

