9.3.4. Other variables

A diagnosis of moderate-to-severe AD is a condition for inclusion into the unexposed cohort. For this registry, moderate-to-severe AD will be defined as an HCP-confirmed diagnosis of AD and the use of a chronic systemic treatment for AD within 1 year prior to DOC. Disease information, including date of diagnosis, previous and current use of chronic systemic treatments for AD, and AD severity will be collected from HCPs.

A comprehensive list of data collected are summarized in Section 9.4.

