- Concurrent pregnancy-related maternal medical conditions or pregnancy complications, including
 - Pregnancy-induced hypertension
 - Pre-eclampsia
 - o Eclampsia
 - Gestational diabetes
 - Preterm labor
 - Placenta previa
 - Placental abruption
 - Incompetent cervix
 - Ectopic pregnancy
 - Molar pregnancy

Maternal Exposures During Pregnancy (reported by the obstetric and/or prescribing HCP)

- Exposure to CIBINQO, including indication/reason for use (FDA-approved or offlabel), dose, route, frequency, and dates/duration of exposure, if available
- Exposure to other drugs or biological products (including prescription and non-prescription drugs, dietary supplements, vaccines, known teratogens, and investigational medications), including indication/reason for use, dose, route, frequency, and dates/duration of exposure, if available
- Exposure to tobacco, alcohol, marijuana, or recreational or illicit drugs, including timing of exposure, if available

Pregnancy Outcome Information (reported by the obstetric and/or pediatric HCP)

- Pregnancy outcome (for each fetus, classified in one of the following mutually exclusive categories: SAB, stillbirth, elective termination, and live birth)
- Date of pregnancy outcome
- Gestational age at pregnancy outcome
- Fetal/infant sex
- Fetal/infant weight, length, and head circumference at pregnancy outcome

PFIZER CONFIDENTIAL Page 32 of 67

- Route of delivery (i.e., spontaneous vaginal delivery, assisted vaginal delivery, or cesarean delivery)
- 5-minute Apgar score
- Congenital malformations (major and minor) and assessment of potential contributing factors
- For a non-induced fetal loss (SAB, stillbirth), factors that may have had an impact on the fetal loss and attribution
- For elective termination, reason (e.g., finding on prenatal test, risk to mother's health, undesired pregnancy)
- Maternal weight at (just prior to) pregnancy outcome

Infant Outcome Information (reported by the pediatric HCP)

- Infant weight, length, and head circumference at birth (if not provided at pregnancy outcome) and at 4 and 12 months of age
- Achievement of the developmental milestones in each Centers for Disease Control and Prevention (CDC)-defined category (social/emotional, language/communication, cognitive, and movement/physical development) at 4 and 12 months of age
- Congenital malformations (major and minor) and assessment of potential contributing factors
- Infant death, including date and cause of death

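### Section 9.7.4 sets overlapping levels (1 and ≥1) for the subgroup by number of systemic therapies in pregnancy, and does not say whether CIBINQO is counted

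*Protocol*

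**What the plan says.** Section 9.7.4 opens with "If sample size permits, subgroup analyses will be conducted" and names four factors: earliest trimester of exposure, cumulative dose, therapy count and maternal age. The therapy count is given as "number of systemic therapy exposures during pregnancy (1 or \geq 1". In the same sentence the age factor is given as "maternal age group at conception (<18, 18 to <35, 35 to <45, and \geq 45 years", four bands that do not overlap and leave no gap.

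The Abstract names the therapy-count subgroup ("number of systemic therapy exposures during pregnancy, and maternal" age group) without levels, so it neither repeats nor corrects those in Section 9.7.4.

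Three other places bear on who can have which count:

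- Section 9.2.1, exposed cohort: "Must receive at least one dose of CIBINQO at any time during pregnancy", or within 1 day before the date of conception (DOC). Sections 9.3.1 and 9.3.3 treat that one-day window as exposure during pregnancy.
- Section 9.3.4, definition of moderate-to-severe AD: an HCP-confirmed diagnosis and "the use of a chronic systemic treatment for AD within 1 year prior to DOC".
- Section 9.2, on comparators: if sample size permits, "a secondary comparator group will include the subset of women with moderate-to-severe AD who are exposed to other chronic systemic treatments" other than JAK inhibitors during pregnancy.

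**The concern.** Levels of a subgroup factor should place each woman in exactly one stratum. Here one level is nested in the other. Results shown side by side for 1 and ≥1 would share all the single-therapy women. The women who differ, those with two or more therapies, would appear only mixed in with the rest. An analyst who followed the text literally would produce strata that are not disjoint. An analyst who noticed the problem would have to choose the levels, possibly after seeing data.

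A second gap sits behind the first. The protocol does not say whether CIBINQO counts as one of the systemic therapies, and the meaning of each level in the exposed cohort depends on that.

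**Working it through.** The protocol attaches no sample size, power or event figure to this subgroup, so there is no stated number to reproduce. The check is to place each possible count k in the levels as written and in disjoint levels.

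| Count k | Levels as written (1; ≥1) | Disjoint levels (0; 1; ≥2) |
|---|---|---|
| 0 | none | 0 |
| 1 | both | 1 |
| 2 | ≥1 only | ≥2 |
| 3 | ≥1 only | ≥2 |
| 4 | ≥1 only | ≥2 |

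As written, only counts of 2 or more fall in exactly one level, and that level also holds every woman with a count of 1.

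**Exposed cohort, CIBINQO counted.** Section 9.2.1 gives every exposed woman a count of at least 1. CIBINQO alone is k = 1 and falls in both levels. CIBINQO plus another systemic drug is k ≥ 2 and falls in ≥1 only. The ≥1 level is therefore the entire exposed cohort.

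**Exposed cohort, CIBINQO not counted.** CIBINQO alone is k = 0 and has no level. CIBINQO plus one other drug is k = 1 and falls in both. CIBINQO plus two or more others falls in ≥1 only. Under this reading the ≥1 level does collect the women on CIBINQO plus something else, but the group they would naturally be set against is missing, and the two levels still overlap.

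**Comparator cohort, if it is split at all.** Section 9.3.4 ties the qualifying systemic treatment to the year before conception, so a comparator may have taken none during pregnancy. Section 9.2 agrees, since comparators treated with other non-JAK systemic drugs in pregnancy are only a subset. The remaining comparators are on none or on another JAK inhibitor. A count of 0 is thus allowed by design and has no level as written. The protocol gives no estimate of how many such women there will be.

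**Are the data there?** Section 9.4 lists "Exposure to other drugs or biological products", with indication and, where available, dates and duration. Current use of chronic systemic AD treatment is also recorded. Disjoint levels need nothing new.

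**The case against.** The best case on the other side is that this is a one-character slip for >1 in a conditional analysis, and that Section 9.7.3 leaves detailed methods to a SAP that may modify the protocol's plans. An error in reading the symbol from the PDF also cannot be fully excluded, although ≥45 in the same sentence reads as it should. All of this bears on how much the point matters. It does not make the text right: the protocol chose to state the levels, and they overlap. Changing the symbol to >1 would cure the overlap but would still leave open whether CIBINQO is counted.

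Several stronger readings are tempting, and the documents do not support them.

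- A reader might infer that the registry cannot separate CIBINQO alone from CIBINQO with other systemic drugs. If CIBINQO is counted, level 1 in the exposed cohort is CIBINQO alone, and crude counts for two or more follow by subtracting level 1 from ≥1. The fault lies in the listed levels, not in the data.
- A reader might infer that a zero level has definitely been left out. Section 9.7.4 does not say which cohort is split. Two of the neighbouring factors, earliest trimester and cumulative dose, describe CIBINQO exposure. If only the exposed cohort is split and CIBINQO counts, level 0 is empty by definition.
- A reader might want to put a number on the dilution. With assumed risks of 3% on one therapy and 9% on two or more, and an assumed share s on two or more, the ratio of ≥1 to 1 is [(1 − s) × 3% + s × 9%] / 3%. That is 1.2 at s = 10%, 1.4 at 20% and 2.0 at 50%, against 9%/3% = 3.0 for disjoint levels. This shows direction only. The protocol gives neither s nor these risks by therapy count, and it plans no ratio of one level to the other.
- A reader might suppose that the subgroup exists to attribute risk to combined immunosuppression. Section 9.7.4 gives no rationale.

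**Conclusion.** The point holds as a wording error in a stated analysis rule. The levels 1 and ≥1 overlap, no level isolates counts of two or more, and no other section puts this right. That part follows from the text alone. What the levels mean in the exposed cohort depends on whether CIBINQO is counted, and they fail either way: ≥1 is then the whole cohort, or CIBINQO-only women have no level. The missing zero level matters for comparators only if that cohort is split too.

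The consequence is minor. It is confined to one subgroup analysis that runs only if numbers allow. The crude proportions of the primary objective, the between-cohort comparison of the secondary objective and the sample size are unaffected. No effect size can be derived from the documents.

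**What to change.** In Section 9.7.4, replace the levels with 1 and ≥2 systemic therapies during pregnancy, and state that CIBINQO is counted. Level 1 in the exposed cohort is then CIBINQO alone, and ≥2 is CIBINQO with at least one other systemic drug. Say whether the comparator cohort is split by the same factor. If it is, add a level 0 for comparators with no systemic therapy during pregnancy.

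The cost is one line of text. The Abstract needs no change because it gives no levels, and no data collection form changes. Making the correction before outcomes by therapy count are examined avoids a post hoc choice of levels. Matching exposed women to comparators on exactly one other therapy is not needed to cure this error; that would be a separate design choice.
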